7.4.7. Clinical Laboratory Assessments

All study-required laboratory assessments will be performed by a central laboratory with the exception of HemoCue Hgb. The results of each HemoCue Hgb must be entered into the subject's eCRF. Details are provided in the SRM.

All laboratory assessments, as defined in Table 12, must be conducted in accordance with the Laboratory Manual and Protocol Time and Events Schedule (Table 10). Laboratory requisition forms must be completed and samples must be clearly labeled with the subject number, protocol number, site/center number, and sample collection date. Reference ranges for all parameters will be provided to the site by the central laboratory. Details of blood sampling (including the volume of blood to be collected) as well as procedures for processing, storage, and shipment of samples are provided in the SRM.

PK assessment of daprodustat is outlined in Section 7.5.

Laboratory assessment		Parameter		
	Platelet count	RBC indices:	WBC dfferential	
	RBC count	MCV	Neutrophils	
IItala	Reticulocyte count	MCH	Lymphocytes	
Hematology	Hemoglobin	MCHC	Monocytes	
	Hematocrit	RDW	Eosinophils	
	WBC count		Basophils	
	Sodium	AST	Bicarbonate	
	Potassium	ALT	Inorganic phosphate	
	Chloride	Creatinine	Glucose	
Clinical chemistry	Calcium (total and albumin- corrected)	Total bilirubin	Direct/indirect bilirubin	
	Albumin	Urea nitrogen		
	Total cholesterol	HDL cholesterol	LDL cholesterol	
	Serum iron	Serum ferritin	Serum transferrin	
Iron parameters	TIBC	UIBC	TSAT	
	Hepcidin			
Other laboratory	FSH ¹	Estradiol ¹	iPTH	
tests	serum hCG ²			
1. Measured in female subjects only to determine the menopausal status (see Section 5.1).				

Table 12 Laboratory Assessments

If additional non-protocol specified laboratory assessments are performed at the institution's local laboratory and result in a change in subject management or are considered clinically significant by the investigator (or subinvestigator) (e.g., SAE or AE or dose modification), the results must be recorded in the eCRF.

Refer to the SRM for appropriate processing and handling of samples to avoid duplicate and/or additional blood draws.

All laboratory tests with values that are considered clinically significantly abnormal during participation in the study should be repeated until the values return to normal or baseline. If such values do not return to normal within a period judged reasonable by the investigator (or subinvestigator), the etiology should be identified and the Sponsor notified.

7.4.8. Ophthalmology

Ophthalmology exams will be performed by a study-designated ophthalmology specialist. Each assessment will include a comprehensive eye exam with at least the following components: measurement of best corrected visual acuity, intraocular pressure, an anterior chamber exam, and a fundoscopic exam. These exams will be used for assessment of ocular adverse events. Assessment results will be captured on worksheets which will be transferred to the eCRF. Additional details on the process for completing these assessments are provided in the SRM.

7.5. Pharmacokinetics

Blood samples for PK analysis of daprodustat will be collected as outlined in Table 11, and the date and time of the last two study medication doses taken prior to blood sampling as well as the date and time of sampling must be recorded in the eCRF.

Measured in female subjects only to determine the menopausal status (see Section 5.1).

Performed in females of childbearing potential.

Blood PK analysis will be performed under the control of GSK Platform Technologies and Science-Drug Metabolism and Pharmacokinetics (PTS-DMPK)/Scinovo and GSK-Japan Bioanalysis, the details of which will be included in the SRM. Concentrations of parent daprodustat will be determined in blood samples using the currently established analytical methodology. Raw data will be archived at the bioanalytical site.

Procedures for processing, storage, and shipment of samples are provided in the SRM.

7.6. Genetics

A blood sample will be collected for genetic analysis from consenting subjects. This sample can be collected on Day 1 once written informed consent has been obtained. Information regarding genetic research is included in Section 12.7. Appendix 7.

7.7. Patient Reported Outcome (PRO)

The patient reported outcome (PRO) [e.g.health-related QOL (HRQoL), health status and health utility] will be assessed using several rating scales.

All questionnaires used in this study have been translated into Japanese and are validated and will be administered in paper version.

Specific instructions on how the subject is to complete the scales and the process for data entry are provided in the SPM.

7.7.1. Health Related Quality of Life (SF-36)

The SF-36 acute version is a general health status questionnaire designed to elucidate the patient's perception of his/her health on several domains, including physical functioning, role physical, bodily pain, vitality, social functioning, role emotional, mental health, and general health over the past seven days. The questionnaire contains 36 Likert type questions that ask the patient to recall how he/she felt during the past seven days.

•

7.7.2. EuroQol 5 Dimension 5 Level Health Utility Index (EQ-5D-5L)/ EuroQol Visual Analogue Scale (EQ-VAS)

The EQ-5D-5L is intended to measure the general health status and health utility. The EQ-5D-5L consists of 2 concepts: self-reported health status consisting of five dimensions (mobility, self-care, usual activities, pain/discomfort, anxiety/depression) each of which can take one of five responses (no problems/slight problems/moderate problems/severe problems/extreme problems) and self-rated health utility on a visual analogue scale (VAS), from 'best imaginable health state' and 'worst imaginable health state'.

8. DATA MANAGEMENT

- For this study subject data will be entered into GSK defined CRFs, transmitted electronically to GSK or designee and combined with data provided from other sources in a validated data system.
- Management of clinical data will be performed in accordance with applicable GSK standards and data cleaning procedures to ensure the integrity of the data, e.g., removing errors and inconsistencies in the data.
- Adverse events and concomitant medications terms will be coded using MedDRA and an internal validated medication dictionary, GSKDrug.
- CRFs (including queries and audit trails) will be retained by GSK, and copies will be sent to the
 investigator to maintain as the investigator copy. Subject initials will not be collected or
 transmitted to GSK according to GSK policy.

9. STATISTICAL CONSIDERATIONS AND DATA ANALYSES

A detailed description of any planned analyses will be documented in a RAP. Any deviations from the analyses described in the protocol will be documented in the RAP or the final study report.

9.1. Hypotheses

The primary objective of the study is to demonstrate the non-inferiority of daprodustat to darbepoetin alfa based on mean Hgb during the primary efficacy evaluation period (Weeks 40 to 52) in HD subjects. As a preliminary assessment, it will be confirmed whether the lower and upper limit of 95% CI for mean Hgb during the primary efficacy evaluation period in daprodustat group would be in target range (10.0-12.0 g/dL) at first. And then the following non-inferiority statistical hypotheses are to be tested at a one-sided significance level of 2.5% (i.e. two-sided significance level of 5%):

- H₀: Treatment difference in mean Hgb during the primary efficacy evaluation period is -1.0 g/dL or less
- H₁: Treatment difference in mean Hgb during the primary efficacy evaluation period is greater than -1.0 g/dL.

Only when the primary endpoint achieves non-inferiority, statistical testing will progress to the principal secondary endpoint with a focus on superiority according to the step-down procedure. More specifically, the superiority of daprodustat to darbepoetin alfa in terms of target Hgb control in HD subjects is to be demonstrated at a two-sided significance level of 5% by testing the following statistical hypotheses:

- H₀: The proportion of subjects whose mean Hgb during the primary efficacy evaluation period is within the target range (10.0-12.0 g/dL) is equal between the treatment groups.
- H₁: The proportion of subjects whose mean Hgb during the primary efficacy evaluation period is within the target range (10.0-12.0 g/dL) is different between the treatment groups.

9.2. Sample Size Considerations

9.2.1. Sample Size Assumptions

Assuming a non-inferiority margin of -1.0 g/dL, a treatment difference of 0.0 g/dL, and a standard deviation of 1.5 g/dL for mean Hgb during the primary efficacy evaluation period in HD subjects, two-sample t-test has at least 99% power at a one-sided significance level of 2.5% (i.e. two-sided significance level of 5%) with a sample size of 100 subjects per group. Assuming a dropout rate of approximately 25%, 135 subjects will be randomized to each group. Given the results from previous non-inferiority studies of similar drugs (darbepoetin alfa, epoetin beta pegol, and peginesatide), the non-inferiority margin of -1.0 g/dL is set. Since an increase of 1.0 g/dL indicates improvement in anemia according to the guidelines for renal anemia in Japan, the non-inferiority margin of -1.0 g/dL may be the clinically acceptable largest difference in renal anemia.

While the present study is designed to ensure long-term safety data from 100 HD subjects, and the primary hypothesis test has at least 99% power to estimate the efficacy very precisely, non-inferiority can be statistically demonstrated with a minimum between-group difference of -0.582 g/dL.

9.2.2. Sample Size Sensitivity

The power is shown according to treatment difference and standard deviation in Table 13.

Table 13 Power Sensitivity (100 Subjects Evaluated, Noninferiority Margin of -1.0, One-Sided Significance Level of 2.5%)

Treatment		Standard deviation	
difference	1.25	1.5	1.75
0	100.0%	99.7%	98.0%
-0.1	99.9%	98.8%	95.1%
-0.2	99.5%	96.4%	89.6%
-0.3	97.6%	90.7%	80.4%

9.2.3. Sample Size Re-estimation or Adjustment

No sample size re-estimation is planned for this study.

9.3. Data Analysis Considerations

9.3.1. Analysis Populations

• All Screening Population

The All Screening Population consists of all subjects who are given subject number and whose data are collected, including demographics at screening.

• Intention-To-Treat (ITT) Population

The ITT Population consists of all subjects who are given a randomization number regardless of whether they actually receive study treatment and whose Hgb assessment was performed at baseline and at least one scheduled post-baseline visit. Subjects will be analyzed according to randomized treatment. This population will be the primary population for an assessment of non-inferiority.

• modified ITT (mITT) Population

The mITT Population consists of all ITT subjects who have at least one Hgb measurement during the efficacy evaluation period. Subjects will be analyzed according to randomized treatment. This population will be the primary population for an assessment of superiority.

• Per-Protocol (PP) Population

The PP Population consists of all mITT subjects who are not major protocol violators. Details will be defined in the RAP. This population will be used for efficacy sensitivity analyses.

Safety Population

The Safety Population consists of subjects who receive at least one dose of study treatment. Subjects will be analyzed according to the treatment received. This population will be used for safety analyses.

• PK Population

The PK Population consists of all daprodustat -treated subjects from whom PK samples are collected and analyzed.

Additional populations may be defined in the RAP.

9.3.2. Interim Analysis

No interim analysis is planned.

9.3.3. Adjustment for Multiplicity

Adjustment for multiplicity will be applied to maintain an overall type I error rate of 5%. After a preliminary assessment, the primary endpoint will be evaluated to demonstrate the non-inferiority at a one-sided significance level of 2.5% (i.e. two-sided significance level of 5%). Only when the primary endpoint achieves non-inferiority, statistical testing will progress to the principal secondary endpoint with a focus on superiority. Since the process will follow step-down manner, a multiplicity adjustment will not be needed according to a closed test procedure, similarly two-sided significance level of 5% will be used.

Other secondary endpoints, which will be evaluated on a complementary or exploratory basis, will be compared at a two-sided significance level of 5% without multiplicity adjustment.

9.4. Key Elements of Analysis Plan

9.4.1. Primary Efficacy Analysis

The primary endpoint, which is the mean Hgb during the primary efficacy evaluation period, will be analyzed to demonstrate the non-inferiority of daprodustat to darbepoetin alfa in HD subjects. MMRM will be used to estimate the mean Hgb during the primary efficacy evaluation period and its 95% CI by treatment groups. This model includes treatment groups, baseline Hgb, assessment visits, interaction terms between treatment groups and assessment visits, as well as interaction terms between baseline Hgb and assessment visit. As a preliminary assessment, it will be confirmed if the lower and upper limit of 95% CI for mean Hgb during the primary efficacy evaluation period in daprodustat group would be in target range (10.0- 12.0 g/dL) at first. This confirmation will be established if the lower and upper limit of 95% CI for the mean Hgb in daprodustat group based on observed Hgb

would lie fully within target range (10.0-12.0 g/dL). In addition, the point estimate and 95% CI for the treatment difference (daprodustat - darbepoetin alfa) in the mean Hgb during the primary efficacy evaluation period will be estimated. Non-inferiority will be established if the lower limit of the 95% CI is greater than -1.0 g/dL. Even if the 95% CI for the difference is completely negative (i.e. lies fully within the range -1.0 to <0 g/dL) non-inferiority would still be concluded on condition that the mean Hgb estimated in the daprodustat group is within the target range.

The primary efficacy population will be the ITT Population, and the analysis will be repeated in the mITT and PP Population to evaluate the robustness of the conclusion. Following sensitivity analyses will be conducted to assess robustness of study result.

- If there are Hgb considered to be impacted by blood transfusion or marketed rhEPO/ESAs, sensitivity analysis excluding the Hgb values from the analyses of primary endpoint will be conducted.
- Analysis of covariance (ANCOVA) will be conducted as sensitivity analysis to MMRM. This
 model includes treatment group and baseline Hgb. The analysis population will be mITT
 population and the similar analysis will be repeated in the PP population.
- A tipping point analysis based on multiple imputation will be conducted as sensitivity analysis to
 missing data assumption. This analysis explores a point where non-inferiority is not confirmed
 (tipping point) by changing assumption to missing data and repeating imputation. The analysis
 population will be ITT population and the similar analysis will be repeated in the mITT and PP
 population.

Further details of sensitivity analyses will be provided in the RAP.

9.4.2. Principal Secondary Efficacy Analysis

The principal secondary endpoint, which is the proportion of subjects whose mean Hgb during the primary efficacy evaluation period is within the target range, will be analyzed to demonstrate the superiority of daprodustat to darbepoetin alfa in HD subjects.

In the mITT Population, a logistic regression model including treatment group and baseline Hgb as covariates will be used to estimate the point estimate and 95% CI for the odds ratio (daprodustat/darbepoetin alfa). This analysis will be performed to demonstrate the superiority at a two-sided significance level of 5%, conditional on the primary endpoint achieving noninferiority. Superiority will be established if the lower limit of the 95% CI for odds ratio is greater than 1.0.

9.4.3. Other Secondary Efficacy Analyses

Among the secondary efficacy endpoints, the time (%) in Hgb target range during the primary efficacy evaluation period , and proportion of subjects who have an Hgb increase of more than 2 g/dL over any 4 weeks, the point estimates and 95% CIs for the treatment difference (or odds ratio) in HD subjects will be calculated. Other secondary efficacy and exploratory endpoints will be summarized by each treatment group.

9.4.4. Safety Analyses

In principle, safety data will be summarized by each treatment group in the Safety Population.

9.4.4.1. Exposure

Exposure information will be listed for all subjects. The duration of treatment (number of days) and cumulative dose will be tabulated. In addition, distribution of the dose level at each assessment visit and final dosing visit will be tabulated. Frequency of dose adjustment and duration of treatment interruption due to Hgb >13.0 g/dL will be summarized.

9.4.4.2. Adverse Events

All AEs will be categorized by the MedDRA system organ class and preferred term to tabulate the number and incidence. All AEs, SAEs, AEs leading to discontinuation of study treatment, and AEs of special interest will be summarized separately. Similar summary will be provided for study treatment-related AEs.

9.4.4.3. Other Safety Parameters

For laboratory tests, vital signs and ECG, parameters and/or changes from baseline will be summarized using summary statistics at each assessment visit. The number and percentage of subjects with values of the potential clinical importance values will be tabulated. The criteria for the potential clinical importance will be described in the RAP. For lipid parameters (total cholesterol, LDL cholesterol, and HDL cholesterol), percent changes will also be tabulated. The number (%) of subjects who have any change in anti-hypertensive medications (type and/or dose) due to increased blood pressure will be tabulated.

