### 8.3.1. Planned Clinical Laboratory Analyses Displays

LDL/HDL cholesterol ratio will be derived from LDL and HDL cholesterol (see Section 15.6.4), and handled as one of chemistry laboratory tests and lipid parameters.

- ***Chemistry/Hematology/Iron Parameter/Other Laboratory Tests***

*Clinical Laboratory Values by Visit*

The values will be summarized using mean, standard deviation, median, minimum, and maximum at each assessment visit and baseline by treatment group. Chemistry, hematology, iron parameter, and other laboratory values will be summarized separately.

*Percent Change from Baseline in Lipid Parameters*

Lipid parameters (including LDL/HDL cholesterol ratio) will be log-transformed and the percent change from baseline will be reported. The percent change from baseline in each lipid parameter, including baseline values, will be summarized using geometric mean, 95% CI, minimum, median, and maximum at each assessment visit by treatment group. In baseline values, the coefficient of variation will also be provided.

*Clinical Laboratory Changes from Baseline by Visit*

The values will be summarized using mean, standard deviation, median, minimum, and maximum at each assessment visit. Change from baseline in chemistry (excluding LDL/HDL cholesterol ratio), hematology, iron parameter, and other laboratory will be summarized separately.

*Worst Case Laboratory Results Relative to Normal Range/PCI Criteria Post-Baseline Relative to Baseline*

The number of subjects with worst case laboratory results relative to normal range/potential clinical importance (PCI) criteria which are post-baseline relative to baseline, including unscheduled assessments, will be summarized by test and category by treatment group. Summaries for normal range and PCI will be provided separately. The categories for normal range are: To Low, To Normal or No Change, To High; the categories for PCI criteria are: To Low, To w/in Range or No Change, To High. The categorization is determined by comparing the baseline category to the worst case post-baseline category. PCI criteria is described in [Appendix 8](#).

- ***Hepatobiliary (Liver)***

Details of liver chemistry stopping criteria are described in the protocol.

Liver monitoring/stopping events will be summarized by treatment group.

Hepatobiliary laboratory abnormalities will be summarized by treatment group.

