## 15.8. Appendix 8: Values of Potential Clinical Importance

### 15.8.1. Laboratory Values

Chemistry			
Laboratory Parameter	Units	Clinical Concern Range	
		Low Flag	High Flag
Albumin (serum)	g/L	< 30 g/L	>55 g/L
Aspartate Aminotransferase	IU/L	N/A	≥ 3x ULRR
Alanine Aminotransferase	IU/L	N/A	≥ 3x ULRR
Bilirubin (total)	μmol/L	N/A	≥ 2x ULRR
Calcium (albumin-adjusted)	mmol/L	< 1.87 mmol/L	> 2.56 mmol/L
Bicarbonate (total)	mmol/L	< 20 mmol/L	> 32 mmol/L
Inorganic phosphate	mmol/L	< 0.81 mmol/L	> 1.77 mmol/L
Potassium (serum)	mmol/L	> 0.5 mmol/L below LLRR	> 1.0 mmol/L above ULRR
Sodium (serum)	mmol/L	< 130 mmol/L	> 150 mmol/L

Hematology			
Laboratory Parameter	Units	Clinical Concern Range	
		Low Flag	High Flag
Platelet Count	GI/L	< 80 GI/L	> 500 GI/L
WBC Count	GI/L	> 1x LLRR	>5x ULRR
Neutrophils	GI/L	< 1.0 GI/L	N/A
Lymphocytes	GI/L	< 0.5 GI/L	N/A

Iron Parameters			
Laboratory Parameter	Units	Clinical Concern Range	
		Low Flag	High Flag
Ferritin	μg/L	< 100 μg/L	> 1200 μg/L
TSAT	%	<15 %	>40 %

Other Parameters			
Laboratory Parameter	Units	Clinical Concern Range	
		Low Flag	High Flag
iPTH	ng/L	N/A	> 9x ULRR

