**CONFIDENTIAL**

201754

Safety Tables					
No.	Population	IDSL / TST ID / Example Shell	Title	Programming Notes	SAC
3.27.	Safety	LB15	Summary of Worst Case Chemistry Results Relative to Normal Range Post-Baseline Relative to Baseline	ICH E3	Y
3.28.	Safety	LB17	Summary of Worst Case Chemistry Results Relative to PCI Criteria Post-Baseline Relative to Baseline	ICH E3	Y
Hematology					
3.29.	Safety	LB1	Summary of Hematology Values by Visit	ICH E3 Includes Baseline values	Y
3.30.	Safety	LB1	Summary of Hematology Changes from Baseline by Visit	ICH E3	Y
3.31.	Safety	LB15	Summary of Worst Case Hematology Results Relative to Normal Range Post-Baseline Relative to Baseline	ICH E3	Y
3.32.	Safety	LB17	Summary of Worst Case Hematology Results Relative to PCI Criteria Post-Baseline Relative to Baseline	ICH E3	Y
Iron Parameters					
3.33.	Safety	LB1	Summary of Iron Parameter by Visit	ICH E3 Includes Baseline values	Y
3.34.	Safety	LB1	Summary of Iron Parameter Changes from Baseline by Visit	ICH E3	Y
3.35.	Safety	LB15	Summary of Worst Case Iron Parameter Results Relative to Normal Range Post-Baseline Relative to Baseline	ICH E3	Y
3.36.	Safety	LB15	Summary of Worst Case Iron Parameter Results Relative to PCI Criteria Post-Baseline Relative to Baseline	ICH E3	Y
Other Laboratory Tests					
3.37.	Safety	LB1	Summary of Other Laboratory Values by Visit	ICH E3 Includes Baseline values	Y
3.38.	Safety	LB1	Summary of Other Laboratory Changes from Baseline by Visit	ICH E3	Y

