**CONFIDENTIAL**

201754

ICH Listings					
No.	Population	IDSL / TST ID / Example Shell	Title	Programming Notes	SAC
Serious and Other Significant Adverse Events					
25.	Safety	AE8	Listing of Fatal Serious Adverse Events	ICH E3	Y
26.	Safety	AE8	Listing of Non-Fatal Serious Adverse Events	ICH E3	Y
27.	All Screening	AE8	Listing of Serious AEs in Screening Period		Y
28.	Safety	AE8	Listing of Adverse Events Leading to Withdrawal from Study / Permanent Discontinuation of Study Treatment	ICH E3	Y
29.	Safety	AE14	Listing of Reasons for Considering as a Serious Adverse Event	ICH E3	Y
30.	Safety	SAFE_L1	Listing of Adverse Events of Special Interest	ICH E3 Displays will be produced with AESI category in addition of AE8 template.	Y
All Laboratory					
31.	Safety	LB5	Listing of All Chemistry Data for Subjects with Any Value Outside of Normal Range/of PCI	ICH E3	Y
32.	Safety	LB5	Listing of All Hematology Data for Subjects with Any Value Outside of Normal Range/of PCI	ICH E3	Y
33.	Safety	LB5	Listing of All Other Laboratory Data for Subjects with Any Value Outside of Normal Range/of PCI	ICH E3	Y

CONFIDENTIAL

201754

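### The WBC low flag for potential clinical importance in SAP 15.8.1 points the wrong way, so Table 3.32 would hide new leukopenia and count recovery as a fall

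*Protocol*

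**What the plan says.** Protocol 9.4.4.3 requires the number and percentage of subjects with PCI values, and delegates the thresholds: "The criteria for the potential clinical importance will be described in the RAP". SAP 8.3.1 sends the reader on to Appendix 8 ("PCI criteria is described in" that appendix). In the hematology block of SAP 15.8.1, the WBC row has a low flag of `> 1x LLRR` and a high flag of `>5x ULRR`.

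The flags feed a shift display. SAP 8.3.1 states that "the categories for PCI criteria are: To Low, To w/in Range or No Change, To High", and that "The categorization is determined by comparing the baseline category to the worst case post-baseline category". Unscheduled assessments are included. For WBC the display is Table 3.32 in SAP 15.10.4.4: "Summary of Worst Case Hematology Results Relative to PCI Criteria Post-Baseline Relative to Baseline".

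No other section gives a different WBC criterion, and the SAP revision history (Section 16) records no change to this cell.

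**The concern.** A low flag should be raised when a count is too low. As printed, this one is raised when the count is above the lower limit and stays silent when it is below. A program that follows the cell literally would still run and fill the WBC row, but the categories would mean the opposite of their labels. The row could look reassuring when subjects had become leukopenic. It could also suggest harm in subjects whose counts had risen. This is a tabulation that the protocol requires, in a study whose results are meant as pivotal data for a Japanese marketing application, so the written rule ought to be right before anyone sees results by arm.

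**Working it through.** **1. Comparison with the other low flags in SAP 15.8.1.** Twelve laboratory parameters carry a low flag.

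- Ten use a less-than sign: albumin, calcium, bicarbonate, phosphate, sodium, platelets, neutrophils, lymphocytes, ferritin and TSAT.
- Potassium uses a greater-than sign, but words it as a distance under the limit: "> 0.5 mmol/L below LLRR".
- WBC uses a greater-than sign with no such word.

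The three vital-sign lower limits in 15.8.2 also use less-than signs. WBC is the only exception.

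**2. The printed rule applied to single values.** Low if WBC > 1 × LLRR; High if WBC > 5 × ULRR; otherwise within range. LLRR and ULRR are read as the lower and upper limits of the reference range.

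| WBC value | As printed | Low-flag sign reversed |
|---|---|---|
| 0.5 × LLRR | within range | Low |
| 0.9 × LLRR | within range | Low |
| equal to LLRR | within range | within range |
| middle of the normal range | Low | within range |
| equal to ULRR | Low | within range |
| 5.5 × ULRR | Low and High | High |

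The result is the same for four assumed reference ranges: 3.0–8.0, 3.5–9.0, 4.0–10.0 and 4.5–11.0 GI/L. It depends on the sign, not on the limits.

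**3. The rule carried into Table 3.32.** Protocol Table 10 schedules the full hematology panel at Day 1 and, on treatment, at Weeks 4, 16, 28, 40 and 52.

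- *Normal at baseline (coded Low), later leukopenic throughout:* every later value is coded within range, so the subject goes to the within-range-or-no-change category.
- *Normal at baseline, leukopenic at some visits only:* any other post-baseline value above the limit is coded Low, so the worst category is Low, the same as baseline. The subject goes to the same category.
- *Below the limit at baseline (coded within range), any later value above it:* counted as moving to Low.
- *Normal throughout:* Low to Low, so no change.

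New leukopenia therefore cannot appear as a move to Low by any route. The only subjects who can appear there are those at or below the limit at baseline who later rise above it.

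**4. Size.** The documents give no numeric WBC limits; Protocol 7.4.7 says only that "Reference ranges for all parameters will be provided to the site by the central laboratory". The figures below rest on assumptions.

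- If a share p of values lies below LLRR, the share flagged Low is 1 − p (ignoring ties). For p = 1%, 2.5%, 5%, 10% and 15% this is 99%, 97.5%, 95%, 90% and 85%.
- With log-normal WBC of mean 6.0 and SD 1.7 GI/L: σ² = ln(1 + (1.7/6.0)²) = 0.0772, so σ = 0.278 and μ = ln 6.0 − σ²/2 = 1.753. P(WBC > LLRR) = Φ((μ − ln LLRR)/σ) is 99.1%, 97.8%, 96.4%, 90.7% and 81.5% for LLRR of 3.0, 3.3, 3.5, 4.0 and 4.5 GI/L.
- These are shares of values, not of subjects shown as moving to Low. If p also applies at baseline, at most 270 × 0.01 = 2.7 to 270 × 0.15 = 40.5 of the 270 planned subjects could be shown as moving to Low, and each of them would have had a rising count.

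**The case against.** The strongest reply is that this is a slip of one sign or one dropped word under a column headed as a low flag, which a programmer would probably notice. Laboratory displays follow the sponsor's core data standards, and the revision history mentions a team review of dry-run output. All of this lowers the chance of a wrong table. It does not supply a rule: the amended SAP still carries the cell, and a programmer who noticed would have to choose the cutoff without written authority. A fault in how the sign was rendered cannot be wholly excluded, but the less-than signs in the platelet, neutrophil and lymphocyte rows are intact.

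The second reply stands in full: leukopenia is not lost from the report. Table 3.31 shows WBC shifts against the normal range, Tables 3.29 and 3.30 give WBC values and changes by visit, and the neutrophil and lymphocyte PCI flags are correctly directed. WBC is not an adverse event of special interest.

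Four stronger readings are tempting, and the documents do not support them.

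- A reader might fault Protocol 9.4.4.3. It only delegates the criteria, which is not an error.
- A reader might infer that Table 3.32 would show nearly everyone as moving to Low. Subjects who are normal throughout fall under no change.
- A reader might infer that Listing 32 would be swamped because of this flag. Its title is "Listing of All Hematology Data for Subjects with Any Value Outside of Normal Range/of PCI", so a value merely outside the normal range is enough. These are anemic subjects entering with hemoglobin of 9.5 to 12.5 g/dL, so most would probably be listed whatever the WBC flag says.
- A reader might suspect the high flag of five times the upper limit as well. Nothing in the documents shows that it is wrong.

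**Conclusion.** The WBC low flag in SAP 15.8.1 is reversed. This follows from the printed text alone, given the ordinary reading of LLRR. If the cell is coded as written, Table 3.32 cannot show new leukopenia as a move to Low, and it presents recovery from a low baseline as one. Between 85% and 99% of WBC values would carry a Low flag if 1% to 15% of values lie below the limit; that range is assumed. The effect is confined to the WBC PCI displays, and no efficacy analysis uses the flag. The point should be corrected, but it does not threaten the trial's conclusions. What the documents cannot settle is the intended cutoff: they establish the direction, not whether one times the lower limit is the right multiple.

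**What to change.** In SAP 15.8.1, change the WBC low flag to a criterion below the limit, for example `< 1x LLRR`, and have the exact cutoff confirmed against the sponsor's PCI standard. The confirmation matters because a cutoff at the limit itself would make the PCI low flag nearly the same as the low side of the normal-range display in Table 3.31. Record the change in the revision history, update the matching program line, and do both before unblinding so that no safety threshold is altered after results are known. The cost is one table cell and one line of code, with no new data.

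The changed line could read: *WBC count: Low Flag `< 1x LLRR` [multiple to be confirmed by the sponsor].*
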